### **1.2 Specific Aims**

1. To demonstrate that UP-CBT is an effective form of therapy for women with lower urinary tract symptoms.
2. To use baseline characteristics in moderation analyses to determine which women will be most likely to have a good response to therapy.
3. To use mediation analyses to test a possible causal chain of events – Does treatment lead to lower anxiety, which in turn leads to fewer urinary symptoms?

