## **2.0 Background / Literature Review / Rationale for the study:**

### **2.1 Gaps in Current Knowledge**

Urinary symptoms are common health issues affecting an individual’s quality of life, including mental health. Urinary symptoms include urgency, frequency, incontinence, nocturia, and overactive bladder. We propose a novel behavioral intervention to improve quality of life in women suffering from urinary symptoms. Many women suffer from urinary symptoms, and these symptoms often cause emotional distress as anxiety and depression are both risk factors for developing urinary symptoms. Similarly, urinary symptoms can be exacerbated by emotional distress. Urinary symptoms and pelvic floor disorders affect nearly one in four women. Women with incontinence are both more likely

to have baseline emotional distress and to develop emotional distress as a result of their incontinence. Yet, current methods to treat incontinence do not address the emotional impact that urinary symptoms may have on women. In fact, one in five women will have surgery for these disorders with 30% needing a second surgery for the same condition. Therefore, more research is desperately needed on non-surgical treatments for these problems that affect millions of women.

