## **2.2 Background**

This study addresses how treatment of overall emotional distress affects anxiety, and in turn urinary symptoms. By experimentally manipulating the trajectory of anxiety through treatment, this study will also give insight into emotional distress as a mechanism of urinary symptoms. Although there is a strong connection between emotional distress and urinary symptoms, evidence on their causal connections remain unexplored. Furthermore, research on cognitive-behavior therapy (CBT) for people with urinary symptoms is lacking. Our study will be the first to apply an empirically-supported, transdiagnostic cognitive- and behaviorally-based treatment to women suffering from urinary symptoms, carried out in accord with high quality psychotherapy trials. The existing evidence base is limited to mindfulness-based stress reduction (MBSR) and physical therapy techniques (e.g., pelvic floor exercises) as treatments for urinary symptoms, which did not address co-occurring symptoms of emotional distress.

Cognitive-behavior therapy has a well-developed protocol and thus can be administered to women of all ages, and of all economic backgrounds. The intervention is time-limited and low-cost, requiring only visits with the behavior therapist and a low-cost workbook that is widely available. This project will also facilitate systemic change by bringing a behavioral intervention directly to the woman, as opposed to asking the patient to schedule appointments in a different location. Delivering cognitive-behavior therapy in the medical setting, such as in primary care, has been used successfully in previous studies, but currently does not exist at Northwestern Medicine. This study can also bring systematic change to the practice of medicine by advancing another possible treatment (i.e., UP-CBT) at the disposal of doctors who are treating women with pelvic floor disorders.

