#### 8.4 Therapy

Participants will be scheduled to come to an individual treatment session once per week for 12 weeks, at a convenient time for them, on the Northwestern Campus. This arrangement allows for a one-stop experience for the patient, maximizing their convenience. As described above, participants will be randomized to one of two therapy conditions: UP-CBT or supportive therapy. All sessions, in both conditions, will be 45 minutes in duration. If a participant happens to miss or cancel a session they will be rescheduled.

Unified-Protocol Cognitive Behavior Therapy (UP-CBT) is a form of therapy that draws upon various forms of cognitive-behavior therapy to “unify” the most important tools into one protocol. Cognitive-behavior therapy has been a leading treatment for depression and anxiety for decades, but historically has focused on specific disorders (e.g., major depression, social anxiety disorder, panic disorder). UP-CBT includes a variety of general-purpose techniques to help people cope more skillfully with emotionally stressful situations. This includes dealing with emotional situations by reappraising negative thoughts (e.g., “If I get nervous at work, the stress I feel will be temporary and won’t kill me” rather than “I can’t deal with my life”). UP-CBT focuses on dealing with stress in general, but its techniques are readily adaptable to dealing with urinary symptoms. For example, a woman might have catastrophic thinking about urine leakage (“What if someone notices that I’ve leaked?”). These catastrophic thoughts can result in strong fear responses, as well as potentially problematic behaviors (e.g., avoidance of social situations or even skipping work). In general, UP-CBT teaches people to track emotions, thoughts, and behavior in an effort to identify maladaptive patterns. In addition, participants learn to restructure their thoughts, and to more confidently confront situations that they find challenging. Towards the end of treatment, patients learn to prevent relapses through practice of therapy skills. Participants in the UP-CBT group will be asked to complete homework outside of the therapy session, to practice therapy skills. Homework will be completed in their therapy workbook, and they will be instructed to bring their workbook to each session. After completing the 12 sessions, participants will be able to keep their workbook.

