**Mediation analysis.** We will also carry out mediation analysis in Mplus using bias-correct bootstrapped 95% confidence intervals. We will hypothesize that these confidence intervals will not contain zero for the following mediated effects:

Condition → Mid-treatment anxiety → Post-treatment urinary symptoms

Condition → Post-treatment anxiety → 3-month urinary symptoms

Condition → 3-month anxiety → 6-month urinary symptoms

In addition to testing statistical significance, our hypothesis is directional. Condition (i.e., receiving UP-CBT) should lead to lower anxiety, in turn leading to lower urinary symptoms.

**Exploratory analyses.** Although our primary focus is anxiety and urinary symptoms, we will conduct HLM analyses on each scale of the PROMIS Profile (depression, fatigue, sleep, pain interference, pain, social function) and other subscales of the PFDI (total score, colorectal symptoms, pelvic organ prolapse symptoms). These analyses will be clearly marked as exploratory in all write-ups. We will also create a prediction model of treatment response (i.e., trajectory of symptoms) based on baseline characteristics. These will also be clearly marked as exploratory in all study write-ups.

Table 3. Project Timeline

	Months 1-2	Months 3-4	Months 5-6	Months 7-8	Months 9-10	Months 11-12	Months 13-14
IRB Approval							
Staff Training							
Recruitment							
Pilot RCT Study							
Follow-up Assessments							
Data Analysis							
Manuscript write-up							

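### The mediation plan tests only anxiety before urinary symptoms and names no urinary covariate, so urinary-first improvement could be reported as anxiety mediation

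*Combined protocol and SAP*

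**What the plan says.** - **Both directions are asserted.** Section 2.1 says "Many women suffer from urinary symptoms, and these symptoms often cause emotional distress" and adds that women with incontinence are more likely "to have baseline emotional distress and to develop emotional distress as a result of their incontinence". It then gives the reverse: "Similarly, urinary symptoms can be exacerbated by emotional distress". Section 2.2 says that "evidence on their causal connections remain unexplored".
- **One direction is tested.** Aim 3 (section 1.2) asks: "Does treatment lead to lower anxiety, which in turn leads to fewer urinary symptoms"? The mediation paragraph of section 8.5 lists three chains. The first is "Condition → Mid-treatment anxiety → Post-treatment urinary symptoms"; the others move the same pattern forward one visit at a time. The hypothesis is directional and the test is a bias-corrected bootstrap 95% interval that excludes zero. No chain runs from urinary symptoms to anxiety, even among the exploratory analyses.
- **Covariates are left open.** The mediation paragraph names none. Section 8.2 mentions demographics as likely covariates, and section 8.3 says outside treatment will be included in analyses. Neither is an earlier UDI-6 or anxiety score.
- **The data exist.** Table 2 (section 8.3) schedules UDI-6 and PROMIS Anxiety at all five assessments.

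**The concern.** Randomisation protects the step from condition to anxiety. It does not protect the step from anxiety to urinary symptoms. Suppose UDI-6 at the mediator's visit drives both anxiety at that visit and UDI-6 at the next. Anxiety then predicts later UDI-6 without affecting it. Measuring the mediator one visit earlier does not break that link. Baseline scores do not break it either, because the common cause includes change after randomisation.

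The protocol itself makes this order plausible, both in section 2.1 and in section 8.4, which says of UP-CBT that "its techniques are readily adaptable to dealing with urinary symptoms".

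Aim 3 is a specific aim, and section 2.2 states that "this study will also give insight into emotional distress as a mechanism of urinary symptoms". Section 14.0 also lists information on the causal link as a benefit. As planned, a significant chain would not separate the hypothesised order from its reverse.

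**Working it through.** **1. The plan's own figure.** Section 4.0 gives d = 1.5, 16 per group analysed, two-sided alpha .05 and power above 98%. With 30 degrees of freedom and noncentrality 1.5 × √(16/2) = 4.24, the noncentral t gives 98.4%. Forty randomised less 20% is 32. Both reproduce. They concern a two-group difference; the documents give no figure for mediation.

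**2. Size of the spurious indirect effect in large samples.** Let therapy lower UDI-6 by d SD, let UDI-6 drive same-visit anxiety with path r, let UDI-6 correlate ρ between visits, and let anxiety have no effect on UDI-6. Then:

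- condition to anxiety: a = −r × d
- anxiety to later UDI-6, within arm: b = r × ρ
- indirect effect: a × b = −r²ρd, a share r²ρ of the total effect −d

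With d = 1.5, r = .5, ρ = .6: a = −0.75, b = 0.30, a × b = −0.225, and 0.225/1.5 = 15%. Over r = .3-.7 and ρ = .4-.8 the share runs from about 4% to 39%. The sign is the one the protocol predicts.

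**3. How often chain 1 would exclude zero at 16 per arm.** The path values are assumptions, because the documents give none. U is UDI-6, A is anxiety, C is condition; 1, 2, 3 are baseline, mid-treatment and post-treatment:

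- A1 correlates .4 with U1
- U2 = .6·U1 − d·C + error (SD 0.8, assumed)
- A2 = .4·A1 + k·U2 + error (SD 0.7), k = .3 to .7
- U3 = .6·U2 − .4·d·C + error (SD 0.8, assumed)
- no path from anxiety to UDI-6

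False anxiety mediation on chain 1 with the planned bias-corrected bootstrap, from two separate runs of this model (run 2 used 600 trials per setting; Monte Carlo standard error at most √(.25/600) = 2.0 points):

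| Direct urinary effect d | As written, run 1 | As written, run 2 | Baseline A and U added, run 2 | Same-visit UDI-6 also added, run 2 |
|---|---|---|---|---|
| 0.5 SD | – | 4-17% | 2-10% | 1-2% |
| 1.0 SD | 9-40% | 10-35% | 6-32% | 2-6% |
| 1.5 SD | 12-60% | 19-62% | 12-47% | 5-9% |

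Run 1 gave 2-10% for the last column over 1.0 and 1.5 SD together. A percentile bootstrap gives lower rates as written: 2-11%, 5-28% and 10-47% for the three effect sizes.

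**4. Chains 1 and 2 together.** This uses the model of step 2, 400 trials per setting and the bias-corrected bootstrap. At d = 1.5 and ρ = .6, at least one interval lies wholly below zero in 17% (r = .3), 54% (r = .5) and 85% (r = .7) of trials; at ρ = .8 and r = .7 it is 94%. Baseline adjustment leaves 39% (r = .5, ρ = .6) and 82% (r = .7, ρ = .8). Same-visit UDI-6 brings these to 6% and 7%. With no therapy effect the rate is 3%.

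**5. If anxiety responds one full visit later.** At d = 1.5, chain 1 is wrong in 1-4% of trials. Chain 2 is wrong in 17% (r = .5, ρ = .6) to 73% (r = .7, ρ = .8).

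**6. What the adjustment costs when the protocol is right.** If anxiety truly drives urinary symptoms within a visit, the chain as written is detected in 64-96% of trials and the same-visit-adjusted chain in 20-43%. A separate run with the percentile bootstrap gave 45-96% and 13-31%. With a one-visit lag the adjusted chain does about as well as the baseline-adjusted one (36-95%).

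**The case against.** This is a pilot of up to 40 women. Mediation is not among the primary analyses, Aim 3 speaks only of a possible chain, and testing the hypothesised direction is a legitimate pre-specified choice. The plan lists path diagrams rather than full equations, so covariates are unspecified, not excluded. All of this is fair. It limits the weight of the point but does not supply the missing analysis, and unlike the exploratory analyses, mediation is stated as a directional hypothesis.

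Three stronger readings are tempting, and the documents do not support them:

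- **That urinary-first improvement would be reported as anxiety mediation.** The rate depends on assumed paths and on anxiety responding within the visit interval. In many of the settings tried, most trials would not report it.
- **That the protocol says UP-CBT lowers urinary symptoms without first lowering anxiety.** Section 8.4 says the techniques can be applied to urinary symptoms, but its leakage example runs through fear and avoidance. It claims no direct effect on UDI-6. The d of 1.5 in section 4.0 is not tied to a named outcome or to a direct urinary route.
- **That the anxiety claim should be allowed only if the chain survives same-visit adjustment.** Step 6 shows that such a gate would usually miss a true within-visit anxiety effect.

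The mirror chains share the weakness. When anxiety truly comes first, the first mirror chain, without same-visit anxiety in the model, falsely excludes zero in 5-49% of trials. They therefore need the matching adjustment.

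**Conclusion.** The concern holds as a possibility, not a certainty. The plan asserts two causal directions, tests one, and names no urinary covariate, so following it exactly would allow a misattribution of order. For chain 1 the assumed range gives roughly 9-40% at a 1.0 SD direct urinary effect and 12-60% at 1.5 SD; at 0.5 SD the risk is much smaller. These figures rest on 16 per arm, paths of 0.3 to 0.7, no anxiety-to-urinary effect, and anxiety responding within the visit interval. A full-visit lag moves the risk from chain 1 to the later chains. None of this shows that anxiety mediation is absent. It shows that a significant stated chain does not by itself establish the order.

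**What to change.** In the mediation paragraph of section 8.5:

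1. Keep the three stated chains and adjust each for baseline anxiety and baseline UDI-6.
2. Pre-specify as sensitivity analyses: (a) each chain with UDI-6 from the mediator's visit also in the outcome equation; (b) the three mirror chains, from condition through UDI-6 to anxiety at the next visit, each also run with anxiety from the mediator's visit in the outcome equation.
3. Report (a) and (b) beside the stated chains, not as a pass/fail gate on reporting them.
4. State in advance that if a stated chain is significant but (a) is not, or the mirror chain is also significant, the result will be described as anxiety and urinary symptoms improving together, with the order not established.
5. State that a null result in (a) will not be read as evidence against anxiety mediation.

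The cost is a few more Mplus runs on scores already scheduled, with no new visits, participants or instruments. The downside is that (a) removes any anxiety effect already complete by the mediator's visit, and so has low power at N = 32 when anxiety acts within a visit.

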Secondary outcomes:						
• PROMIS Profile (29 items)	5-10 min	X	X	X	X	X
• PGI-I	< 1 min			X	X	X

Secondary correlates:						
• PTSD Checklist for DSM-5 with Life Events Checklist (PCL-5)	10 min	X				
• Mini-IPIP	3-5 min	X				
• Ruminative Response Scale (RRS)	1-3 min	X				
• Follow-up treatment questions	1-3 min				X	X

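### The three mediation chains use anxiety as the only mediator, so a positive result cannot separate an anxiety path from a correlated depression or general-distress path

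*Combined protocol and SAP*

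**What the plan says.** Aim 3 (section 1.2) is "To use mediation analyses to test a possible causal chain of events", running from treatment to anxiety to urinary symptoms. Section 8.5 carries this out as "mediation analysis in Mplus using bias-correct bootstrapped 95% confidence intervals". The first chain is "Condition → Mid-treatment anxiety → Post-treatment urinary symptoms". The other two move the mediator to post-treatment and 3 months, and the outcome to 3 and 6 months. The stated reading is "Condition (i.e., receiving UP-CBT) should lead to lower anxiety, in turn leading to lower urinary symptoms". No second mediator, covariate or sensitivity analysis is named for these models.

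Other sections describe a wider mechanism:

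- Section 2.1: "anxiety and depression are both risk factors for developing urinary symptoms".
- Section 2.2: "this study will also give insight into emotional distress as a mechanism of urinary symptoms".
- Section 8.4, in introducing UP-CBT: "Cognitive-behavior therapy has been a leading treatment for depression and anxiety for decades".

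Section 8.3 includes depression in the PROMIS Profile, and Table 2 schedules the Profile at all five assessments. In section 8.5 the depression score appears only as an outcome in exploratory HLM analyses.

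**The concern.** On the protocol's own account, treatment may lower depression as well as anxiety, and depression may affect urinary symptoms. If the two scores are correlated within arm, leaving depression out of the outcome model lets the anxiety coefficient absorb part of depression's effect. Randomising therapy protects the comparison of arms. It does not protect the step from mediator to outcome. Measuring the mediator one visit before the outcome does not help either, because depression at that earlier visit precedes the outcome equally.

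What is at stake is the conclusion for Aim 3. An interval that excludes zero could be read as evidence that lowering anxiety is what improves urinary symptoms, when the data fit a depression or general-distress path as well.

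**Working it through.** **1. The plan's own figure.** Section 4.0 gives 16 per group, d = 1.5, two-sided alpha .05 and power above 98%. The noncentrality is 1.5 × √(16/2) = 4.243. The normal approximation gives Φ(4.243 − 1.960) = Φ(2.283) = 98.9%, and the exact noncentral t gives 98.4%. Enrolment also agrees: 40 × (1 − 0.20) = 32. These figures reproduce. No power figure is given for mediation.

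**2. Bias in a single chain.** Let C be the arm, and scale anxiety (A), depression (D) and urinary symptoms (U) to a within-arm SD of 1. Suppose A = −aC + e_A and D = −aC + e_D, with correlation r between e_A and e_D, and U = bD + error. Anxiety then has no effect on U. Regressing U on C and A alone gives an anxiety coefficient that tends to b·r, so the estimated indirect effect tends to −a·b·r instead of 0. The true effect through depression is −a·b. The fraction credited to anxiety is therefore r.

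With a = 1.5, b = .5 and r = .6, the false anxiety effect is −1.5 × .5 × .6 = −0.45 SD, out of −1.5 × .5 = −0.75 SD. Sample size does not enter, so more women would not remove it.

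**3. How often the interval misleads.** The analysed n of 16 per arm and a = 1.5 (borrowed from the sample-size d) come from section 4.0. The values of r, b, the alternative a = 0.8 and the equal effect on both scores are assumptions. The simulation used 600 trials per setting and 1,000 bias-corrected bootstrap resamples, with residual variance 1 − b². Monte Carlo SE is at most √(.5 × .5/600) = 2.0 points. Entries are the percentage of trials in which one anxiety-only chain lies wholly below zero, when depression is the only mediator:

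| a | b | r = 0 | .3 | .5 | .7 | .8 |
|---|---|---|---|---|---|---|
| 1.5 | .3 | 4.5 | 10.3 | 19.3 | 28.3 | 30.3 |
| 1.5 | .5 | 4.0 | 19.7 | 34.3 | 57.7 | 68.0 |
| 1.5 | .7 | 4.7 | 30.3 | 56.0 | 85.7 | 93.2 |
| 0.8 | .3 | 3.3 | 7.0 | 13.0 | 19.8 | 23.8 |
| 0.8 | .5 | 3.5 | 12.5 | 27.0 | 39.3 | 54.0 |
| 0.8 | .7 | 3.0 | 21.3 | 39.8 | 58.5 | 66.5 |

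The nominal rate in one direction is 2.5%. With 20 per arm, the 57.7% becomes 66.3%, as expected of bias. A second simulation at a = 1.5, b = .5 gave 21%, 38% and 66% at r = .4, .6 and .8. It gave 7% at a = 0.8, b = .3, r = .4. With percentile intervals and residual SD 1, the rate at a = 1.5, b = .5, r = .6 was 30%.

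**4. Adding depression.** With D in the outcome model, the anxiety coefficient tends to 0 under step 2. Over the same settings the anxiety-specific interval falls below zero in 2.0% to 5.8% of trials.

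**5. Cost when anxiety is the true mediator.** Adding D multiplies the standard error of the anxiety coefficient by about 1/√(1 − r²), which is 1/√.64 = 1.25 at r = .6 and 1/√.36 = 1.67 at r = .8. At a = 1.5, b = .5, detection falls from about 85% to 66% at r = .6, and from 83% to 45% at r = .8. With b = .3 and r = .7 it falls from 46% to 28%.

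**6. Depression downstream of anxiety.** Suppose therapy lowers anxiety, anxiety lowers depression (D = rA + error), and depression lowers urinary symptoms. Aim 3 is then true. The single chain again tends to −a·r·b = −0.45 SD at the step 2 inputs, while the anxiety-specific path in the parallel model tends to 0. In simulation the anxiety path was found in 39–44% of trials without depression and in 4–7% with it.

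**The case against.** Anxiety is a reasoned, prespecified choice. An anxious presentation or history is required for entry, whereas depression is not. Anxiety is one of two primary outcomes and the mediator named in Aim 3, and section 2.2 describes the route as running through anxiety. The trial is a pilot, and section 8.5 does not say that anxiety acts to the exclusion of depression. All of this stands, and it is why the three chains should stay.

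A reader might infer that the protocol treats depression as an equal risk factor. It does not: section 2.1 says that both are risk factors and does not rank them. A reader might also infer that a false anxiety finding is the usual outcome. The documents cannot support that, because they give no anxiety–depression correlation, no path size and no expected effect on depression. At the weaker inputs the rate is about 7%.

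The objection to making any mediation claim conditional on the parallel model also stands. The loss of power in step 5 is real with 32 women, and the structure in step 6 would lead such a rule to withhold a correct conclusion. Falling back on a distress conclusion without a test would be no better. In one simulation with anxiety as the sole mediator at r = .6 (residual SD 1), neither specific path excluded zero in 43% of trials. A joint indirect effect therefore has to be reported.

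What the objection does not remove is that the planned model, read causally, cannot tell the two paths apart.

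**Conclusion.** The point holds as a limit on what Aim 3 can conclude. An anxiety-only chain that excludes zero is compatible with mediation through anxiety, through depression, or through general distress. If depression were the only true mediator, one chain would mislead in roughly 7% to over 60% of trials, and in up to 93% at the most extreme setting examined (a = 1.5, b = .7, r = .8). That range rests on assumed correlations of .3 to .8, paths of .3 to .7 SD, and equal treatment effects of 0.8 or 1.5 SD on both scores. The direction of the bias does not depend on the exact values, provided that the correlation is positive, treatment lowers anxiety, and higher depression worsens urinary symptoms.

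The documents do not show that anxiety is the wrong mediator or that depression is the right one. A null anxiety-specific path in the parallel model would not refute Aim 3. The two primary outcome models are unaffected.

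**What to change.** Keep the three anxiety chains as planned. Beside each, prespecify a sensitivity model with PROMIS Depression at the mediator's visit (mid-treatment, post-treatment, 3 months) as a parallel mediator. Report the anxiety-specific, depression-specific and total (joint) indirect effects together, and fix the wording in advance:

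- If the anxiety path holds in the parallel model, the mechanism may be called anxiety-specific relative to depression.
- If it does not, but the total indirect effect or the single-mediator chain excludes zero, report mediation through anxiety or correlated emotional distress that this trial cannot separate.
- If neither the total effect nor the single chain excludes zero, claim no mediation.

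State two limits in the plan. About 32 women give low precision for separating the paths (step 5). Depression may also lie downstream of anxiety, so a null anxiety-specific path is not evidence against Aim 3 (step 6).

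The change needs one extra variable per Mplus model, already collected at every assessment, and no new visits or questionnaires. The cost is a wider interval for the anxiety-specific path and a more guarded conclusion when the two scores move together.
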